## E. Methods

### Measures

**Sitting.** Our primary outcome measures are the average number of minutes sitting per day and the number of sitting bouts  $>30$  minutes during waking hours over one week measured with activPAL (PalTechnologies, Glasgow, Scotland). ActivPAL is superior in estimation of postural changes (sitting vs. standing) compared to other monitors partly due to thigh placement. It is waterproofed for 7+ days by placing in a nitrile sleeve and wrapping in medical adhesive before attaching to the thigh with medical adhesive (i.e., can be worn while bathing). The device estimates time in sitting, standing, or stepping postures and transitions (sit-to-stand, stand-to-sit) in 15 second epochs. It is small, lightweight, and unobtrusive. Its rechargeable batteries last up to 14 days. We have successfully collected pilot data from 100 older adults establishing safety and **feasibility** including adhesive integrity for the study duration. Participants will be educated on use of the device before recording data. Logs will be used to record waking/sleeping times and problems with or removal of monitors (see appendices).

**Biomarkers.** Fasting and postprandial glucose and insulin will be collected to determine whether changes in sedentary behavior impact glycemic control and insulin sensitivity. Postprandial glucose and insulin responses will be determined as reported previously. Briefly, an IV catheter will be placed for sampling by a nurse. Fasting baseline blood will be drawn. Subjects will then consume a liquid mixed meal (Ensure drink containing 57% carbohydrate, 28% fat, and 15% protein). Blood will then be collected at 15, 30, 45, 60, 90, and 120 minutes after consumption of the drink. The total amount of blood will not exceed 92 cc which is safe for adults over 100 lbs. Glucose will be measured in all samples immediately after collection with a glucose analyzer (YSI 2300 Stat plus). Remaining blood will be processed with centrifugation and serum separated and stored at -80 until time of analysis. Insulin will be measured in serum using Enzyme-Linked Immunosorbent Assay (ELISA; Alpco Diagnostics). Glucose and insulin area under the curve calculations will quantify postprandial responses. We will calculate insulin sensitivity via the Matsuda index as reported previously. Body mass will be measured using a digital scale. Height will be measured by stadiometer with shoes off. Waist circumference will be reported as the average of 3 measures.

**Covariates.** Covariates include age, sex, education, marital status, physical functional limitations, health history, self-reported pain, and medications that may influence insulin sensitivity and glycemic control. We will classify medications into categories of drugs used to treat diabetes or to induce weight loss, and use them as covariates in the model to determine the effect of the intervention on biomarkers after adjusting for use of these classes of medications.

Inclusion Criteria	Exclusion Criteria
1) Person with MCI enrolled in KU ADC Registry	1) Unable to stand or walk unassisted
2) Clinical Dementia Rating (CDR) = 0.5 for the impaired partner	2) Inadequate visual, auditory, or English language capacity
3) Inactive status on MOST questionnaire (both partners)	3) Adhesive allergy
4) Retired or $<20$ hrs/wk in an office (both partners)	4) Current Type 2 diabetes
5) Live together in a community dwelling setting (both partners)	5) Unwilling to change sitting behavior

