We will use a multi-level model to evaluate the change in our outcome variables across three time points. Level 1 is time of observation (baseline, mid-study, follow up). Level 2 is the individual (with or without MCI), and Level 3 is the level of the dyad. This model includes the non-independence in the estimation of the two members of the dyad as well as repeated observations for each individual. This model also allows us to compare whether individuals with MCI are equally or less responsive to the intervention than the study partners within the context of the dyadic relationship. Constraining estimates to be equivalent provides a test of the significance of the difference in the estimates between the MCI patients and the study partners. We are primarily interested in the change in outcome measures (listed below) from pre-intervention to post-intervention (i.e., is the intervention effective), thus we are testing for a growth model with an intercept change, indicating a mean change after the intervention, this type of model can estimate discontinuous processes with longitudinal data. With regard to the multiple time points, we hypothesize an improvement in outcomes from baseline to mid-point and a maintenance effect from mid-point to follow up. Outcomes are (1) average daily sitting time (2) number of sitting bouts  $>30$  min (3) insulin and glucose, adjusting for baseline values and relevant covariates (disability status, medications, age, education, etc.). Data will be validated for wear time (i.e. remove periods of sleep or monitor removal). A valid day of wear is  $\geq 10$  hours of waking wear time and a valid week of wear includes  $\geq 4$  valid days of wear ( $\geq 1$  weekend day).

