## Procedures

**Pre-Intervention (T0).** Eligibility will be determined via chart review and telephone screening.

**Baseline Visit (V1).** Participants (both the individual with MCI and the study partner) will arrive fasting for baseline insulin and glucose testing. Weight, height, and waist circumference will be measured for both partners. Postural monitors will be attached by study staff to participants' dominant thigh. Participants will be asked not to remove the monitor for 7- 24 hour periods. They will receive instructions on use of the monitors and sleep/wake logs.

Table 2.	Pre-	Pre-	Pre-	Int	Int	Int	Int	Int	Int	Post-	Post-
			Wk0	Wk1	Wk2	Wk5	Wk 6	Wk8	Wk12	Wk13	Wk14
Study Timeline	T0	V1	BL	HI1	TI1	HI2	M	TI2	HI3	FU	V2
Eligibility Screening	X										
Insulin & Glucose		X									X
Postural monitoring			X				X			X	
Postural feedback				X							X
Education & goals				X							
Wrist worn alert				X	X	X	X	X	X		
Intervention Visit				X	X	X		X	X		

T- telephone; V- clinic visit; BL- Baseline; HI- Home intervention visit; M-Mid-Study; FU- Follow up

**Baseline Postural Monitoring (BL).** Participants will wear monitors for 1 week and return it at the home visit (HI1). They are encouraged to call the clinic regarding questions about monitors or sleep logs.

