## **V. Data Analysis and Reporting**

### **Statistical and Data Analysis:**

**Data Analysis:** We will use a multi-level model to evaluate the change in our outcome variables across three time points. Level 1 is time of observation (baseline, mid-study, follow up). Level 2 is the individual (with or without MCI), and Level 3 is the level of the dyad. This model includes the non-independence in the estimation of the two members of the dyad as well as repeated observations for each individual. This model also allows us to compare whether individuals with MCI are equally or less responsive to the intervention than the study partners within the context of the dyadic relationship. Constraining estimates to be equivalent provides a test of the significance of the difference in the estimates between the MCI patients and the study partners. We are primarily interested in the change in outcome measures (listed below) from pre-intervention to post-intervention (i.e., is the intervention effective), thus we are testing for a growth model with an intercept change, indicating a mean change after the intervention, this type of model can estimate discontinuous processes with longitudinal data. With regard to the multiple time points, we hypothesize an improvement in outcomes from baseline to mid-point and a maintenance effect from mid-point to follow up. Outcomes are (1) average daily sitting time (2) number of sitting bouts >30 min (3) insulin and glucose, adjusting for baseline values and relevant covariates (disability status, medications, age, education, etc.). **Outcome:** Milestones for achieved **feasibility** include successful recruitment and retention of participants, 10% or less of technological failures, rate of participant concerns addressed by phone and at home visits, acceptability of the intervention to participants (measured by questionnaires HI3), and few adverse events. Effectiveness of the intervention will be evaluated based on change of moderate effect size in the average amount of time spent in sitting and duration of sitting bouts as demonstrated in previous studies. Two previous intervention studies reported a decline in sitting time of about 3 - 4%. We will use this range as our target for success.

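### The second primary outcome, sitting bouts over 30 minutes, has no stated per-day unit although a valid week may hold 4 to 7 valid days; read literally, the count moves with wear as well as with behaviour

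*Combined protocol and SAP*

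**What the plan says.** Section II.E, Measures (Sitting), names both primary outcomes in one sentence: "Our primary outcome measures are the average number of minutes sitting per day and the number of sitting bouts", the bouts being those longer than 30 "minutes during waking hours over one week measured with activPAL". The first carries an explicit daily average and the second does not.

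The outcome list in Sample Size, Statistical Methods, & Power and in section V, Statistical and Data Analysis, keeps the contrast: "Outcomes are (1) average daily sitting time (2) number of sitting bouts >30 min".

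The wear rule appears in Sample Size, Statistical Methods, & Power. Sleep and non-wear are removed. A day must have 10 or more waking hours recorded to count. For the week, the rule is that "a valid week of wear includes $\geq 4$ valid days of wear", including at least one weekend day. The upper limit comes from Procedures: "Participants will be asked not to remove the monitor for 7- 24 hour periods". An accepted week can therefore contribute 4, 5, 6 or 7 valid days.

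Nowhere is the bout count divided by valid days or wear hours, rescaled to seven days, or given an offset. Wear is not among the covariates named in Measures or in the analysis sections, although the analysis lists are left open-ended.

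**The concern.** Averaging per day puts sitting minutes on the same scale whatever the number of valid days. A total over the valid days of a week does not have that property: a lost day removes that day's bouts. Fewer valid days after the intervention would look like improvement, and more would hide it.

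Three features of the study make this worth settling.

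- It is a single-arm pre-post study (section II.B defers a control group to later work), so no comparator would show a drift in wear.
- Monitors are handled differently by occasion: at baseline attached in clinic and handed back at the first home visit, at mid-study mailed back, after week 13 returned to the clinic. Waking time rests on participant logs. Equal numbers of valid days are possible, but the plan should not depend on them.
- The model is meant to test whether people with MCI respond as much as their partners. A change in valid days that differs by role would enter that comparison directly.

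**Working it through.** The documents state no expected count, standard deviation or power for the bout outcome, so there is no figure of the plan's to reproduce. The check is direct arithmetic.

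**Inputs.** From the documents: 4 to 7 valid days in an accepted week; at least 10 waking hours in a valid day. Assumed: days failing the rule contribute no bouts, and a person's rate *r* of bouts per valid day is constant.

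**1. One person, unchanged behaviour.** Weekly count = *r* × *d* for *d* valid days. The change against a full week is *d*/7 − 1, and *r* cancels.

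| Valid days | Change against 7 days | Count at assumed *r* = 3 / 5 / 8 |
|---|---|---|
| 7 | 0% | 21 / 35 / 56 |
| 6 | 6/7 − 1 = −14.3% | 18 / 30 / 48 |
| 5 | 5/7 − 1 = −28.6% | 15 / 25 / 40 |
| 4 | 4/7 − 1 = −42.9% | 12 / 20 / 32 |

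In the other direction, 4 days at baseline and 7 afterwards gives 7/4 − 1 = +75%.

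**2. Group mean.** If valid days are unrelated to *r*, the spurious change in the mean is (mean days after)/(mean days before) − 1. The following means are assumptions, since the documents give none:
- 6.5 to 6.5 days: 0%
- 6.5 to 6.25 days: 6.25/6.5 − 1 = −3.8%
- 6.5 to 6.0 days: 6.0/6.5 − 1 = −7.7%
- 6.0 to 6.5 days: 6.5/6.0 − 1 = +8.3%

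Equal loss at both occasions leaves the mean percentage change intact. If people with MCI went from 6.5 to 6.0 days and partners stayed at 6.5, the two roles would appear to differ in response by 7.7 percentage points with no difference in behaviour.

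**3. Noise when mean wear is equal.** If valid days have standard deviation *s* at each occasion, independently, they add *r* × *s* × √2 to the standard deviation of individual change. With an assumed *s* = 0.8, this is 3 × 0.8 × 1.414 = 3.4 bouts at *r* = 3, 5.7 at *r* = 5 and 9.1 at *r* = 8. Extra spread of this kind shrinks a standardised effect.

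**4. Simulation check.** There was no behaviour change, 200,000 simulated people, an assumed mean of 5 bouts per day, 7 valid days at baseline, and later days lost at random (at most 3). Mean losses of 0.35, 0.70 and 1.36 days changed the raw count by −5.1%, −9.9% and −19.5%. Bouts per valid day changed by no more than 0.1% in each case.

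**5. What division by days leaves.** A valid day may hold 10 waking hours of wear or more. Against an assumed waking day of 14 to 16 hours, with bouts evenly spread, 10 hours lowers the day's count by 1 − 10/14 = 28.6% to 1 − 10/16 = 37.5%. Dividing by valid days does not remove this.

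**The case against.** The strongest reply is that the wording is ambiguous. The words about waking hours over one week can be read as the recording window for both measures, since sitting minutes are also recorded for a week, and a daily mean may be intended for both. The outcome lists elsewhere give bouts no time unit, so they do not establish a weekly total either. This stands in part: a reader might infer that the plan has fixed a raw weekly total, and the text does not go that far. But no section states a daily rate for bouts, and a plain reading of the definition together with the wear rule yields a total. The unit of a primary outcome should not be left to interpretation.

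Second, wear may be nearly complete. The monitor is waterproofed, fixed with adhesive and attached by staff, and its battery lasts up to 14 days. Preliminary Results reports technological problems preventing valid data in only 5% of 100 pilot participants. This also stands, and it makes the 43% case an extreme. It does not show how valid days are spread among usable weeks, and the 4-day minimum itself allows for incomplete ones.

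Third, section V judges effectiveness on time spent sitting and duration of bouts, not on the bout count, and the study is a feasibility pilot of 15 dyads declared underpowered. So the effectiveness criterion as worded is not directly affected. The count remains one of the two declared primary outcomes and a listed model outcome.

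Finally, a reader might set the percentages above against the 3–4% target in section V. That target is stated for the decline in sitting time, which is already a daily average. It is not a yardstick for bout counts.

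**Conclusion.** The point holds as a defect in the outcome definition. Read literally, the bout count is proportional to valid days and is 14%, 29% or 43% lower at 6, 5 or 4 days than at 7 with no change in behaviour. This rests on a constant daily rate and on failed days contributing nothing; it does not depend on the bout rate.

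A reader might infer that the trial will report a false improvement. The documents do not support that: they give no distribution of valid days and no evidence that wear falls over time, so neither the size nor the direction of any bias can be computed. The mean change is biased only if valid days shift systematically between occasions, and the comparison of people with MCI and partners only if they shift differently by role. Without such shifts the cost is noise, which still matters because the pilot's declared purpose for this aim is an effect size. The outcome should be redefined before analysis.

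**What to change.** In Measures, in Sample Size, Statistical Methods, & Power, and in section V, Statistical and Data Analysis, define the second primary outcome as the mean number of sitting bouts longer than 30 minutes per valid day, computed over the valid days of each monitoring week. This puts it on the same footing as sitting minutes and keeps the planned multilevel model.

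Also standardise to waking wear hours, at least as a sensitivity analysis: for example, bouts per waking wear hour, or waking wear hours as a covariate. The same wear-hours adjustment is worth applying to sitting minutes, which also depend on how much of the day was recorded.

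Report the number of valid days and waking wear hours by occasion and by role, so that any shift in wear is visible.

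A count model with log exposure (valid days or wear hours) as an offset is an alternative, but it changes the model family and would need to be specified as such.

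The cost is a short wording change in three places and one added sensitivity analysis. The monitor data and logs already planned supply everything needed.

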## Procedures

**Pre-Intervention (T0).** Eligibility will be determined via chart review and telephone screening.

**Baseline Visit (V1).** Participants (both the individual with MCI and the study partner) will arrive fasting for baseline insulin and glucose testing. Weight, height, and waist circumference will be measured for both partners. Postural monitors will be attached by study staff to participants' dominant thigh. Participants will be asked not to remove the monitor for 7- 24 hour periods. They will receive instructions on use of the monitors and sleep/wake logs.

Table 2.	Pre-	Pre-	Pre-	Int	Int	Int	Int	Int	Int	Post-	Post-
			Wk0	Wk1	Wk2	Wk5	Wk 6	Wk8	Wk12	Wk13	Wk14
Study Timeline	T0	V1	BL	HI1	TI1	HI2	M	TI2	HI3	FU	V2
Eligibility Screening	X										
Insulin & Glucose		X									X
Postural monitoring			X				X			X	
Postural feedback				X							X
Education & goals				X							
Wrist worn alert				X	X	X	X	X	X		
Intervention Visit				X	X	X		X	X		

T- telephone; V- clinic visit; BL- Baseline; HI- Home intervention visit; M-Mid-Study; FU- Follow up

**Baseline Postural Monitoring (BL).** Participants will wear monitors for 1 week and return it at the home visit (HI1). They are encouraged to call the clinic regarding questions about monitors or sleep logs.

**Home and Telephone Intervention Visits (HI1-3, TI1-2).** A series of home visits and telephone calls will be used to administer the behavioral intervention for both members of the dyad together. Study staff will be trained on intervention procedures by [name] via two 1-hour Skype training sessions and a written handbook based on his expertise in sitting reduction interventions. At the first intervention visit (**HI1**), participants will receive preliminary feedback on baseline monitoring (i.e., graphical & verbal feedback, attention to times of day when sitting occurred), and will be mailed a more detailed account of their sitting behavior to review at **TI1**. The education and goal setting session will consist of 1) education on demographic trends, harms of sitting, contexts in which prolonged sitting occurs, recommendations for reduced sitting, 2) guided completion of a workbook that: a) asks participants to reflect on their habits, b) sets realistic and measureable goals, describes expectations for change in sitting and barriers to reducing sitting, c) evaluates perceived benefits of reducing inactivity, reinforcement strategies for rewarding change and enjoyable nonsedentary activities to pursue, ratings of confidence in ability to make changes, d) tips for ways to reduce sitting time (targeted to individual habits and home environments), and ways to make sitting time more active when sitting cannot be avoided. In the home, interventionists and participants will identify specific environmental cues that promote sitting and devise plans to integrate nonsedentary activity into typical routines. The workbook was originally developed by [name] et al. based on Social Cognitive Theory and Behavioral Choice Theory.

Both members of the dyad will receive a water resistant activity monitor to wear on the non-dominant wrist (Jawbone Up, San Francisco, CA). Monitors will be programmed to provide vibrations ("idle alerts") to encourage activity after inactive periods of >30 minutes and to shut off during hours when participant is normally asleep. We chose Jawbone for programmability and vibration reminders (vs. auditory). Jawbone batteries last 10 days. Participants and study partners will be trained in their home on how to recharge them and can be assisted via telephone and during home visits if needed. Participants and study partners will indicate in logs during which activities they most frequently received alerts to assist in goal setting during subsequent visits.

TI1 (wk2) will focus on problems and adherence with idle alerts, monitor wear, success of limiting sitting to 30 minutes, and goals for other cues to limit sitting. HI1 (wk5) will focus on setting goals for replacing sitting with standing/light activity, maintenance of goals, and reduction of barriers. Study staff will attach activPAL monitors for mid-intervention assessment of changes in sitting time in both partners (**M**) measured during week 6 of the intervention. After the weeklong assessment, participants will mail monitors in a pre-addressed stamped padded envelope. TI2 (wk8) will check on success of goal maintenance and barrier reduction. HI2 (wk12) will be the final follow up visit to address barriers and discuss progress toward

maintaining goals. Questionnaires will be used to assess the acceptability of the intervention to participants. Study staff will attach activPAL monitors for post-intervention assessment of changes in sitting time (measured week 13).

**Follow up (V3).** Participants will return monitors to the clinic and complete follow up biomarker testing (glycemic control, insulin resistance, BMI, and waist circumference). Participants will receive feedback from postural monitoring during the waiting period of glucose testing.

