Interventions targeting sedentary behavior can effectively reduce sitting time (average 42 min/day), but few studies have evaluated whether these reductions result in clinically meaningful outcomes and none have been conducted in older adults with MCI. **We propose a feasibility study of a 12-week home based behavioral intervention to reduce sitting time among sedentary older adults with MCI and their caregivers.** The intervention is designed to break up prolonged bouts of sitting and replace sitting behavior with standing and light or moderate intensity activities associated with improved cognitive performance among people at risk for AD. Our proposed intervention adds innovative elements that are empirically rigorous compared to previous studies: 1) it uses objectively assessed electronic postural monitoring, 2) it provides electronic feedback to promote sitting times <30 minutes, 3) it assesses insulin sensitivity and glycemic control which are sensitive to changes in sitting after a short duration and which few previous interventions have measured, 4) it is conducted in the home and targeted to individual habits and physical environments that reinforce sitting behaviors, 5) it targets sedentary older adults with MCI, which has not been done before, and 6) it capitalizes on the caregiver/patient dyad to help improve adherence to the behavioral change regimen.

**Specific Aim 1: Determine feasibility of a 12-week home and telephone based intervention in older adults with mild cognitive impairment targeting both the impaired individual and their study partner to help initiate and maintain behavior change.** We will recruit KUADC registry participants with MCI and their caregivers (as study partners). Behavioral interventions are more effective when there is built in social support. We will evaluate feasibility in terms of successful recruitment and retention of participants, 10% or less of technological failures, rate of participant concerns addressed by phone and at home visits, acceptability of the intervention to participants (measured by questionnaires during home visits).

**Specific Aim 2: Determine whether a 12-week home and telephone based intervention results in reduced total sitting time and shorter bouts of sitting in older adults with MCI and their caregivers.** Electronic postural monitors will record sitting time for a duration of one week at three time

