points (pre-intervention, mid-intervention, and post-intervention). The intervention includes 1) feedback from baseline monitoring, 2) educational and goal setting session with the participants and research staff, 3) wrist worn monitors that alert wearers to sitting times >30 minutes, 4) home and telephone visits to address physical, psychological, and home environment barriers to behavior change. Changes in sitting time and breaks from sitting will be compared between baseline, mid-intervention, and post-intervention measurement occasions.

**Specific Aim 3: Determine whether sedentary behavior intervention results in improved insulin sensitivity and glycemic control.** To evaluate whether reduced sitting results in meaningful metabolic changes, we will measure postprandial insulin and glucose, and body composition, and evaluate changes from pre- to post- intervention adjusting for relevant covariates.

The PI is an early-career investigator who has completed KU-ADC funded pilot work using objective activity monitoring and has the necessary foundation for the proposed research on physical activity and sedentary behavior in older age and AD. She has several published papers on biomarkers associated with cognitive decline and dementia. She has successfully collaborated with the KU-ADC since 2008 to build a program of research measuring physical activity in naturalistic settings in older adults with and without AD. She has experience in use, interpretation, and analysis of objective activity monitoring data in ADC participants. Her pilot work found that participants with mild AD did not differ from older adult controls in their levels of moderate physical activity, but differed in sedentary and light intensity activities. This supports the idea that sedentary behavior is a valuable target for this population.

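### The wrist alert and a primary outcome share the same 30-minute cut, so standing only when alerted does not lower the count of sitting bouts over 30 minutes and can raise it

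*Combined protocol and SAP*

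**What the plan says.** All references are to the combined protocol and SAP.

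- **Alert.** Procedures (section II.E) has the wrist device vibrate "to encourage activity after inactive periods of >30 minutes and to shut off during hours when participant is normally asleep". Specific Aim 2 (section I.A) describes the same devices as "wrist worn monitors that alert wearers to sitting times >30 minutes". Earlier in section I.A the stated purpose is different: "it provides electronic feedback to promote sitting times <30 minutes".
- **Outcome.** Measures (section II.E) says "Our primary outcome measures are the average number of minutes sitting per day and the number of sitting bouts" longer than 30 minutes, taken from the activPAL over one week. The data analysis part of section V repeats this: "Outcomes are (1) average daily sitting time (2) number of sitting bouts >30 min (3) insulin and glucose". The sample size and statistical methods section has the same list.
- **Resolution.** On the activPAL: "The device estimates time in sitting, standing, or stepping postures and transitions (sit-to-stand, stand-to-sit) in 15 second epochs".
- **Aim and success criterion.** Aim 2 asks whether the intervention "results in reduced total sitting time and shorter bouts of sitting in older adults with MCI and their caregivers". Section V judges effectiveness by a moderate effect size in sitting time and in how long bouts last, with a target decline in sitting time of about 3 to 4%. Neither statement refers to a count.
- **Timing.** Table 2 marks the wrist alert from week 1 to week 12, including the week 6 monitoring. It does not mark it at the week 13 monitoring.

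**The concern.** The prompt and the counted event use the same cut. If someone sits still for the whole period and gets up when the wrist vibrates, the thigh monitor has already recorded more than 30 minutes of unbroken sitting. With 15-second epochs, even a quick response can be classed as over the limit. If the person then sits down again, a long bout becomes several bouts, more than one of which may pass 30 minutes.

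The count therefore cannot separate a participant who ignores the alerts from one who follows them, and it can move against the intended direction when the alert works. The plan concedes that Aims 2 and 3 are underpowered and relies on effect sizes, which are meant to support an application for a larger randomised trial. An effect size near zero or of the wrong sign on a named primary outcome would be hard to interpret, and the single-arm design has no control group to help explain it.

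**Working it through.** The documents give no bout count, bout-length distribution or power calculation for this outcome, so there is no stated figure to reproduce. The check is simple counting.

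**Inputs from the documents.** Alert after more than 30 minutes; outcome counts bouts over 30 minutes; 15-second epochs; alert in use in weeks 1 to 12.

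**Assumptions (not in the documents).** Baseline bout length L; minutes seated before standing on the alert, T, from 30.25 to 35; break b of 0 to 5 minutes, after which the person sits again for the rest of the same period.

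**Formula.** Each cycle takes T + b minutes, and a piece counts if more than 30 minutes of the period remain when it starts. For L > 30 and T > 30:

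count after = (L − 30) / (T + b), rounded up.

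This is at least 1, so a baseline bout over 30 minutes never drops out of the count through alert adherence alone. The result is 2 or more once L > T + b + 30. That point is 61 minutes for T = 31, b = 0 and 70 minutes for T = 35, b = 5.

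**Example day, bouts of 60, 60, 90 and 120 minutes (330 in total), T = 31, b = 0.**

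- 60 min: 30/31, rounded up = 1 (twice)
- 90 min: 60/31 = 1.94, rounded up = 2
- 120 min: 90/31 = 2.90, rounded up = 3
- Count: 4 before, 1 + 1 + 2 + 3 = 7 after (+75%)

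With T = 35, b = 5, the ratios are 30/40, 60/40 and 90/40, and the count is again 7.

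**Duration measures on the same day (T = 31, b = 0).**

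- Minutes in bouts over 30 min: 330 before, 7 × 31 = 217 after
- Pieces: 2 + 2 + 3 + 4 = 11, so mean bout length goes from 330/4 = 82.5 to 330/11 = 30.0 min
- Total sitting: 330 before and after; any break b > 0 lowers it

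Splitting a bout cannot raise the minutes spent in long bouts, and it cannot raise the mean over all bouts. Neither measure can reverse through this mechanism.

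**Sensitivity.**

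| Assumed baseline bouts (min) | T, b (min) | Count before | Count after |
|---|---|---|---|
| eight of 60 | 31, 2 | 8 | 8 |
| 180, 120, 90, 45, 20, 20, 20 | 31, 2 | 4 | 11 |
| 240, 180, 120 | 31, 2 | 3 | 15 |
| any of these, standing at or before 30 | 30, 2 | as above | 0 |
| 60, 60, 90, 120, not sitting again after the first alert | 31, – | 4 | 4 |

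In the second row total sitting falls from 495 to 473 minutes (22/495 = 4.4%), minutes in bouts over 30 fall from 435 to 341, and mean bout length falls from 70.7 to 26.3 minutes. Such a participant would pass the plan's 3 to 4% target on one primary outcome while the other nearly triples.

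**The case against.** The best reply is that the plan does not judge success on the count. Section V uses sitting time and bout length, and both move the right way in every split example, or at worst stay level for total sitting. A reader might infer that a rise in the count would be declared a failure of the intervention; the documents do not support that. What remains is that the count is still a named primary outcome, and that it matches neither the aim nor the success criterion.

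Second, the plan's main interest is the change from before to after the intervention, and Table 2 does not mark the alert at week 13. This stands: the direct effect is on week 6. It is not wholly excluded at week 13, because habits may persist and participants may keep the devices. Week 6 also matters in its own right, since the plan hypothesises its improvement between baseline and mid-point.

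Third, the alert is only one component. The first telephone call reviews "success of limiting sitting to 30 minutes, and goals for other cues to limit sitting", and the workbook and home visits work on other prompts to stand. People who get up before 30 minutes lower the count. This also stands, and the point concerns adherence to the alert alone.

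Fourth, the rise rests on assumed bouts well over 60 minutes and on sitting down again soon. That is correct. It would also be wrong to say that every piece of a split bout counts, since the last piece is often under 30 minutes.

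Finally, one might infer that the wrist timer always starts late, because it senses inactivity rather than posture. The documents do not say so. Wrist movement while seated could delay the alert, and stillness before sitting could bring it forward.

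**Conclusion.** The point holds in a limited form. Following the alert alone does not lower the count of bouts over 30 minutes. It leaves the count unchanged for baseline bouts up to about 60 minutes (61 to 70 across the main response and break times tried) and can raise it for longer ones, from 4 to 7 in the example. This assumes that the alert comes after more than 30 minutes of actual sitting and, for a rise, that the person soon sits again. The baseline bout lengths are illustrative.

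This is a possibility, not a forecast that the count will rise in this trial. The documents do not support the stronger reading that the trial's effectiveness conclusion would be reversed, because that conclusion rests on sitting time and bout length. Severity is moderate: one primary outcome is poorly aligned with the intervention and with Aim 2, while total sitting time, the other primary outcome, is not subject to the reversal.

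**What to change.** In Measures, in the sample size and statistical methods section, and in section V:

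- Replace the count as the primary bout outcome with one duration-based measure: minutes per waking day accumulated in bouts over 30 minutes, or mean bout length. Name one before the data are seen. The first keeps the 30-minute cut and cannot rise through splitting, though it remains sensitive near the cut (217 minutes when standing at 31, 0 when standing at 30). Mean bout length is 30.0 minutes in both cases.
- Keep the number of bouts over 30 minutes as a secondary description, and state that it may stay flat or rise under adherence to the alert.
- Reconcile the under-30-minute purpose in section I.A with the alert trigger in Specific Aim 2 and Procedures. State whether the alert is active during the week 13 monitoring.

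The cost is outcome wording and one more summary from the same activPAL files, with no new data. The primary bout measure becomes slightly less comparable with studies that report the count over 30 minutes; the secondary measure preserves that comparison.
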